1.1 Scope of document

The Statistical analysis plan (SAP) describes the implementation of the statistical analysis planned in the protocol.

1.2 Study reference documentation

Final study protocol (V03) is available at the time of finalization of Statistical Analysis Plan Amendment 1.

1.3 Study objectives

1.3.1. Primary objective(s)

Primary objective(s)	Endpoints related to primary objectives

 To determine the safety and tolerability of LMB763 during 12 weeks of treatment. 	
 Safety endpoints (including vital signs, physical examination, laboratory measurements, ECG). Adverse events.

 To determine the effect of LMB763 on circulating alanine aminotransferase (ALT) levels. 	
 Liver function tests.

1.3.2. Secondary objective(s)

Secondary objective(s)	Endpoints related to secondary objective(s)

 To evaluate the pharmacokinetics (PK) of LMB763 in NASH patients. 	
 PK blood collection and analysis (Cmax, Tmax, AUC, Racc, etc.).

 To determine the effect of LMB763 on intrahepatic lipid after 12 weeks of treatment. 	
 Percent (%) Liver fat as measured by Magnetic Resonance Imaging (MRI).

 To determine the effect of LMB763 on anthropometric assessments after 12 weeks of treatment. 	
 Weight, BMI, waist-to-hip (WTH) ratio.

 To determine the effect of LMB763 on non-invasive markers of liver fibrosis. 	
 Fibroscan[®] (in a subset of patients) Enhanced liver fibrosis panel (ELF) and fibrosis biomarker test (originally known as Fibrotest[®]/FibroSure[®]).

 To determine the effect of LMB763 on fasting lipid profile. 	
 Fasting lipid profile.

• To determine the effect of LMB763 compared with placebo with respect to occurrence and impact of potential itch.	
• Itch scored on 100 mm visual analog scale (VAS) ratings.
--	--

Corporate Confidential Information

[figure not shown]
1.4 Study design and treatment

This is a non-confirmatory, multicenter, patient and investigator blinded, randomized, placebo-controlled, parallel group study, in two cohorts, in patients with NASH.

For cohort 1, the study will consist of a screening period of 45 days, baseline period of 14 days, treatment period of 12 weeks, followed up by a study completion evaluation approximately 28 days after the final drug administration.

For cohort 2, the study will consist of a screening period of 40 days, baseline period of 20 days, treatment period of 12 weeks, followed up by a study completion evaluation approximately 28 days after the final drug administration.

Figure 1-1: Study Design – Cohort 1

[figure not shown]
^aPatients will be randomized in a 2:1 ratio to receive LMB763 100 mg (n ~ 64) or matching Placebo (n ~ 32). Study medication will be self administered by patients once daily for 12 weeks. On visit days, study medication will be administered at the site. If additional dosing arms are included, the same study design will be followed.

^bEOS evaluation to be completed approximately 28 days after the final study drug administration (i.e. Day 112 (± 2 days))

^cTreatment randomization may occur prior to day 1 as soon as patient eligibility is confirmed from baseline assessments

^dAll visit during the treatment and follow-up periods will have a window of ± 2 days

Figure 1-2: Study Design – Cohort 2

^aPatients will be randomized in a 2:1 ratio to receive LMB763 (n ~ 64) or matching Placebo (n ~ 32). Study medication will be self administered by patients once daily for 12 weeks. On visit days, study medication will be administered at the site.

^bEOS evaluation to be completed approximately 28 days after the final study drug administration (i.e. Day 112 (± 2 days))

^cTreatment randomization may occur prior to day 1 as soon as patient eligibility is confirmed from baseline assessments

^dAll visit during the treatment and follow-up periods will have a window of ± 2 days

2 First interpretable results (FIR)

First interpretable results (FIR) will be provided for this trial.
Corporate Confidential Information

FIR will focus on the following analyses:

- Analysis populations
- Subject disposition
- Demographics and baseline characteristics. Baseline characteristics include, but are not limited to:
 - Liver function tests: ALT
- Safety results include but are not limited to:
 - Number and percentage of subjects with adverse events by system organ class
- Pharmacokinetic (PK) results for plasma:
 - Arithmetic mean (SD) concentration-time plot per treatment (overlying).
 - Summary statistics for PK parameters.
- Pharmacodynamic (PD) analyses include, but are not limited to:
 - Treatment response at Week 12 in ALT
 - Mean (SE) ALT plot per treatment (overlying) over time
 - Treatment comparison of key secondary parameters (Percent liver fat as measured by MRI, Weight, Fibroscan[®], ELF panel, fasting lipid profile and itch as assessed on the VAS scale) at Week 12

- Mean (SE) plots of key secondary parameters (Percent liver fat as measured by MRI, Weight, Fibroscan[®], ELF panel, fasting lipid profile and itch as assessed on the VAS scale) per treatment (overlying) and over time.

Corporate Confidential Information

4 Statistical methods: Analysis sets

For all analysis sets, subjects will be analyzed according to the study treatment(s) received. All placebo subjects will be pooled. Subjects with dose frequency/dose change due to AE will be analyzed according to the treatment they received up to the dose frequency/dose change.

All patients that received at least one dose of study drug will be included in the safety data analysis “safety population”.

The PK analysis set will include all subjects with at least one available valid (i.e., not flagged for exclusion) PK concentration measurement, who received any study drug and experienced no protocol deviations with relevant impact on PK data.

All patients with evaluable PD parameter data and no major protocol deviations impacting PD data will be included in the PD data analysis “PD population”.

For the End of Study (EOS) visit only data from study completers will be included in the summary/analysis tables/figures.

The data exclusion for each analysis set based on protocol deviation codes will be captured in the following table, which will be completed in a SAP amendment prior to DBL as needed.

Table 4-1 Protocol deviation codes and analysis sets

Category Deviation code	Text description of deviation	Data exclusion
	Subjects are excluded from all (safety) analysis in case of these protocol deviations:	Exclude subject completely from all (safety) analysis sets
	Subjects are excluded from PK analysis in case of these protocol deviations:	Exclude subject from PK analysis set
	Subjects are excluded from PD analysis in case of these protocol deviations:	Exclude subject from PD analysis set
	Subjects are excluded from PK/PD analysis in case of these protocol deviations:	Exclude subject from PK/PD analysis sets

5 Statistical methods for Pharmacokinetic (PK) parameters

5.1 Variables

The following pharmacokinetic parameters will be determined for each analyte using the actual recorded sampling times and non-compartmental method(s) with Phoenix WinNonlin (Version 6.2 or higher): C_{max}, T_{max}, AUC_{last}, AUC_{tau}, R_{acc}, T_{1/2}, V_z/F and CL/F from the plasma concentration-time data.

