IEC	Independent Ethics Committee
IRB	Institutional Review Board
IRT	Interactive Response Technology
LDH	lactate dehydrogenase

LFT	Liver function test
LLN	lower limit of normal
LLQ	lower limit of quantification
MedDRA	Medical dictionary for regulatory activities
mg	milligram(s)
mL	milliliter(s)
MRI	Magnetic resonance imaging
NASH	Non-alcoholic steatohepatitis
NCDS	Novartis Clinical Data Standards
o.d.	once a day
p.o.	Oral
PA	posteroanterior
PD	pharmacodynamic(s)
PK	pharmacokinetic(s)
RBC	red blood cell(s)
RDC	Remote Data Capture
REB	Research Ethics Board
SAE	serious adverse event
sCR	serum creatinine
SD	standard deviation
SGOT	serum glutamic oxaloacetic transaminase
SGPT	serum glutamic pyruvic transaminase
SOM	Site Operations Manual
SUSAR	Suspected Unexpected Serious Adverse Reactions
TBL	total bilirubin
ULN	upper limit of normal
ULQ	upper limit of quantification
WBC	white blood cell(s)
WHO	World Health Organization
WTH	Waist to hip

Pharmacokinetic definitions and symbols

AUC _{last}	The area under the plasma (or serum or blood) concentration-time curve from time zero to the time of the last quantifiable concentration [mass x time / volume]
AUC _{tau}	The area under the plasma (or serum or blood) concentration-time curve from time zero to the end of the dosing interval tau [mass x time / volume]
CL/F	The apparent systemic (or total body) clearance from plasma (or serum or blood) following extravascular administration [volume / time]
C _{max}	The observed maximum plasma (or serum or blood) concentration following drug administration [mass / volume]
R _{acc}	The accumulation ratio
T _{1/2,acc}	The effective half-life based on drug accumulation at steady state [time]
T _{max}	The time to reach the maximum concentration after drug administration [time]
V _{z/F}	The apparent volume of distribution during the terminal elimination phase following extravascular administration [volume]

Glossary of terms

Assessment	A procedure used to generate data required by the study
Cohort	A specific group of subjects fulfilling certain criteria
Control drug	Any drug (an active drug or an inactive drug, such as a placebo) which is used as a comparator to the investigational drug being tested in the trial
Dosage	Dose of the study treatment given to the subject in a time unit (e.g. 100 mg once a day, 75 mg twice a day)

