5.2 Descriptive analyses

LMB763 and LMB763 metabolites ^{Corporate Confidential Information} plasma concentrations will be listed by treatment, subject, and visit/sampling time point. Descriptive summary statistics will be provided by treatment and visit/sampling time point. Summary statistics will include mean (arithmetic and geometric), SD, CV (arithmetic and geometric), median, minimum, maximum, and the frequency (n, %) of concentrations below the LLOQ. Concentrations below LLOQ will be treated as zero in summary statistics and for PK parameter calculations. A geometric mean will not be reported if the dataset includes zero values. Graphical methods will be employed to show mean and individual concentration-time profiles.

Pharmacokinetic parameters will be listed by treatment and subject and summarized by treatment with descriptive statistics as listed above. Since T_{max} is generally evaluated by a nonparametric method, only median, minimum, and maximum will be reported.

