5.3 Statistical model, assumptions and hypotheses

Dose proportionality

An exploratory assessment of dose proportionality for LMB763 and LMB763 metabolites ^{Corporate Confidential Information} will be conducted. Log-transformed dose-normalized Day 1 and Day 42 AUC and C_{max} will be analyzed separately using an Analysis of Variance (ANOVA) with dose as the classification factor. A comparison between the 2 doses will be made within the ANOVA framework. The ratio of geometric means and the associated 90% confidence interval (CI) will be obtained by back-transforming the least squares mean treatment difference and the corresponding 90% CI in the log domain to the original scale.

6 Statistical methods for Pharmacodynamic (PD) parameters

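### SAP 5.1, on its visible text, derives CL/F and Vz/F for LMB763 metabolites as well as for LMB763; for a metabolite, which is never dosed, these are not the parameters the protocol defines

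*SAP*

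**What the plan says.** SAP 5.1 sets the scope of the non-compartmental analysis: "The following pharmacokinetic parameters will be determined for each analyte using the actual recorded sampling times". The list is Cmax, Tmax, AUClast, AUCtau, Racc, T1/2, Vz/F and CL/F, all taken "from the plasma concentration-time data".

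SAP 5.2 identifies the analytes as "LMB763 and LMB763 metabolites"; the words that follow are redacted. It then reports the parameters without distinguishing between analytes: "Pharmacokinetic parameters will be listed by treatment and subject and summarized by treatment with descriptive statistics as listed above". SAP 5.3 adds "An exploratory assessment of dose proportionality for LMB763 and LMB763 metabolites", but that model uses only AUC and Cmax.

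The protocol's list of pharmacokinetic definitions gives CL/F as "The apparent systemic (or total body) clearance from plasma (or serum or blood) following extravascular administration", and describes Vz/F in parallel terms as the apparent terminal-phase volume after extravascular dosing. Protocol 6.1.1 and 6.1.2 show that only LMB763 or placebo is given. Protocol 11.5.2 carries the same parameter list, but it speaks of LMB763 plasma concentrations and mentions neither metabolites nor several analytes.

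**The concern.** CL/F and Vz/F both relate a known administered dose to the resulting exposure. For the parent the dose is known and only bioavailability, F, is left in the denominator. For a metabolite the amount entering the body is itself unknown, because it depends on how much parent is converted. If the LMB763 dose is divided by the metabolite AUC, the result mixes formation with elimination but is labelled as clearance.

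The parameter list appears to have been carried from the parent-only setting of Protocol 11.5.2 to every analyte, without removing the two entries that do not carry over. At stake is the meaning of two rows in the metabolite tables and of any exploratory look that uses them. SAP section 8 may relate UGT1A1 polymorphism to PK parameters, and Protocol 5.2 treats UGT1A1 inhibition as relevant to LMB763 metabolism. If a measured metabolite is formed partly by UGT1A1 (an assumption, since the metabolites' identities are not visible), a genotype that lowers formation would raise its so-called CL/F and look like faster elimination.

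**Working it through.** The plan states no figure on this point, so there is none to reproduce. The check is a mass balance, confirmed with a numerical parent–metabolite model (linear, first-order absorption, one compartment each).

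**Inputs from the documents.** The parameter list and its scope (SAP 5.1); metabolites as analytes (SAP 5.2, 5.3); the definitions of CL/F and Vz/F (Protocol, pharmacokinetic definitions); concentrations in mass per volume (Protocol 8.7); LMB763 or placebo as the only dosed substances (Protocol 6.1).

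**Assumed inputs, for illustration only.** Dose 100, F = 0.8, absorption rate constant 1/h, parent CL = 10 L/h and V = 50 L, metabolite CLm = 5 L/h and Vm = 20 L, fm from 0.05 to 1.0.

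**Step 1, parent.** AUC = F × Dose / CL, so Dose/AUC = CL/F = 10/0.8 = 12.5 L/h. The model returns 12.5 at every fm. The parameter is valid for LMB763.

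**Step 2, metabolite clearance.** The amount formed is F × fm × Dose, so AUCm = F × fm × Dose / CLm and Dose/AUCm = CLm/(F × fm). The quantity the label suggests is CLm/F = 5/0.8 = 6.25 L/h.

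| fm (assumed) | Dose/AUCm (L/h) | Ratio to CLm/F = 1/fm | (Dose/AUCm)/λz (L) | Ratio to Vm/F = 25 L |
|---|---|---|---|---|
| 0.05 | 125.0 | 20 | 630 | 25.2 |
| 0.1 | 62.5 | 10 | 315 | 12.6 |
| 0.3 | 20.8 | 3.3 | 105 | 4.2 |
| 0.5 | 12.5 | 2 | 63 | 2.5 |
| 1.0 | 6.25 | 1 | 31.5 | 1.26 |

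The ratio equals CLm/F only if all absorbed drug becomes that one metabolite.

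**Step 3, metabolite volume.** Vz/F is computed as (Dose/AUCm)/λz, and the true Vm/F is 20/0.8 = 25 L. Even at fm = 1 the result is 31.5 L. The fitted terminal slope, 0.198/h, follows the parent's rate constant (10/50 = 0.2/h) rather than the metabolite's own (5/20 = 0.25/h). The extra factor is 0.25/0.198 = 1.26. It depends on which process is slower. At fm = 0.3:

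- CLm = 20 L/h (metabolite rate constant 1.0/h): the slope is 0.2/h and Vz/F is 416.7 L. That is 16.7 times 25 L, made up of 3.33 for fm and 5 for the slope.
- CLm = 1 L/h (metabolite rate constant 0.05/h): the slope is 0.05/h and Vz/F is 83.3 L. That is the fm factor of 3.33 alone.

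So Vz/F always carries 1/fm and carries a second distortion only when formation limits the terminal phase. In that case metabolite T1/2 also describes formation rather than metabolite elimination.

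**Step 4, mass units.** Without conversion to moles, the metabolite value is also multiplied by the parent-to-metabolite molecular-weight ratio. No molecular weights are visible, so this factor cannot be sized.

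**Step 5, formation read as elimination.** With CLm unchanged, moving fm from 0.5 to 0.3 takes Dose/AUCm from 12.5 to 20.8 L/h. That is a 67% rise (20.83/12.5 = 1.67) with no change in elimination.

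**The case against.** The best case for the plan has four parts.

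- **Redaction.** Text is blacked out directly after the mention of metabolites in SAP 5.2 and 5.3. Protocol 11.5.2 sends the reader to Section 8.7 for the calculations, and that section has redacted blocks. A parent-only limit or a metabolite-specific definition could sit there. The SAP also prints no formula, so dose over AUC is an inference. This stands as a limit on certainty. However, the scope sentence in SAP 5.1 is visible and contains no limit. Protocol 11.5.2 also withholds CL/F when the terminal fit is poor, which is consistent with a derivation from dose and AUC.
- **Convention.** The definitions say apparent, and do not say that the dose must be of the analyte itself. Some reports let F absorb fm for metabolites. The visible documents neither adopt nor exclude that convention. If it is meant, it has to be stated.
- **Use.** No planned inference uses these values. Dose proportionality uses AUC and Cmax, and the PK/PD exploration names Cmax and AUCtau. If F × fm is constant, it cancels from between-dose ratios. Parent CL/F likewise confounds F with clearance. All of this stands and keeps the point small.
- **Safeguard.** The rule on adjusted R² in Protocol 11.5.2 may suppress some values, but it does not change what the reported ones mean.

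A reader might infer that the secondary PK objective is compromised. The documents do not support that: the objective concerns the PK of LMB763, whose CL/F and Vz/F are correctly defined. Nor do they support reading Vz/F as off by 1/fm alone; Step 3 of the working shows why.

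**Conclusion.** The point holds as a definitional correction of modest weight. Following SAP 5.1 as visible, metabolite CL/F would estimate CLm/(F × fm), with a molecular-weight factor in mass units. Metabolite Vz/F would carry the same factor, plus a further distortion wherever the terminal slope is limited by formation.

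This rests on dose over AUC being the formula used, on linear kinetics, and on the redacted text containing no restriction. The 2-, 3.3- and 10-fold figures follow from chosen values of fm. They illustrate the mechanism and should not be read as effect sizes for this trial.

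The reach is limited to listings and summaries of metabolite parameters, which may enter the first interpretable results, and to exploratory use such as UGT1A1 polymorphism against PK parameters. Even there the wording of SAP section 8 leaves open which parameters are meant. Metabolite Cmax, Tmax, AUC and Racc remain usable. Parent PK, the dose-proportionality analysis, the ALT analyses, power and the safety analyses are unaffected.

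**What to change.** Amend SAP 5.1 so that CL/F and Vz/F are derived for LMB763 only, with the other parameters kept for all analytes. If the sponsor wants to keep the two for metabolites, label them CLm/(F × fm) and its volume analogue, define them in the SAP, and compute them from the molar dose. In either case, describe metabolite T1/2 as an apparent terminal half-life that may reflect formation. If a restriction already exists in the redacted text, repeating it in SAP 5.1 is enough.

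The cost is one or two sentences before the tables are programmed, and the first option removes output rather than adding it. The labelling option needs the molecular weights. Sample size, alpha and data collection do not change. Molar metabolite-to-parent ratios of AUC and Cmax would be informative, but they are an optional addition and not part of this correction.

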5.2 Descriptive analyses

LMB763 and LMB763 metabolites ^{Corporate Confidential Information} plasma concentrations will be listed by treatment, subject, and visit/sampling time point. Descriptive summary statistics will be provided by treatment and visit/sampling time point. Summary statistics will include mean (arithmetic and geometric), SD, CV (arithmetic and geometric), median, minimum, maximum, and the frequency (n, %) of concentrations below the LLOQ. Concentrations below LLOQ will be treated as zero in summary statistics and for PK parameter calculations. A geometric mean will not be reported if the dataset includes zero values. Graphical methods will be employed to show mean and individual concentration-time profiles.

Pharmacokinetic parameters will be listed by treatment and subject and summarized by treatment with descriptive statistics as listed above. Since T_{max} is generally evaluated by a nonparametric method, only median, minimum, and maximum will be reported.

5.3 Statistical model, assumptions and hypotheses

Dose proportionality

An exploratory assessment of dose proportionality for LMB763 and LMB763 metabolites ^{Corporate Confidential Information} will be conducted. Log-transformed dose-normalized Day 1 and Day 42 AUC and C_{max} will be analyzed separately using an Analysis of Variance (ANOVA) with dose as the classification factor. A comparison between the 2 doses will be made within the ANOVA framework. The ratio of geometric means and the associated 90% confidence interval (CI) will be obtained by back-transforming the least squares mean treatment difference and the corresponding 90% CI in the log domain to the original scale.

6 Statistical methods for Pharmacodynamic (PD) parameters

6.1 Primary objective

One of the primary objectives of this study is to assess the efficacy of LMB763 in NASH patients during 12 weeks of treatment.

6.1.1 Variable

Change from baseline in ALT is the primary efficacy variable. Baseline is defined as the mean of ALT levels at Baseline (V2) and pre-dose (V101) visits.

6.1.2 Descriptive analyses

The absolute and change from baseline as well as percent change from baseline ALT measurements will be listed by treatment, subject and visit/time and descriptive statistics will be provided by treatment and visit/time. Summary statistics will include mean (arithmetic and geometric), SD, CV (arithmetic and geometric), median, minimum and maximum as appropriate.

Mean (SE) absolute and change from baseline ALT as well as geometric mean ratio to baseline ALT (90% CI) over time will be plotted by treatment.

6.1.3 Statistical model, assumptions and hypotheses

Bayesian approach

A Bayesian approach will be used to analyze the change from baseline to Week 12 in ALT, which is assumed to follow a normal distribution with a known variance for each treatment arm. An informative prior for the placebo treatment effect and a non-informative prior for the LMB763 treatment effect will be incorporated in the analysis. The variance and the informative prior will be based on historical control data from external and/or internal studies such as the FLINT trial (Neuschwander-Tetri et al 2015). Median estimates, 90% credible intervals and posterior probabilities that the placebo-adjusted ALT reduction by an LMB763 dose is (a) greater than 0 and (b) greater than 19 U/L and/or another cutoff value will be provided within the Bayesian framework.

The cohort effect will be explored and a cohort-wise analysis may be performed as needed.

If placebo data from in-house studies in a similar patient population become available they may be included in an ANCOVA on log-transformed data via informative priors.

Repeated measures approach

A repeated measures analysis of covariance (ANCOVA) will be performed for change from baseline ALT. The model will include effects for treatment, visit, treatment by visit interaction, stratification factor (BMI group), baseline, and baseline by visit interaction. The BMI group will have the following 2 strata: low BMI (Asian <30 and Non-Asian <35) and high BMI (Asian ≥ 30 and Non-Asian ≥ 35). An unstructured variance-covariance structure will be used to account for correlation among multiple measurements from the same patient and variance heterogeneity. If the unstructured covariance causes model convergence issues other simpler covariance structures will be considered. Point estimates, the associated two-sided 90% confidence interval as well as the p-values for treatment differences (including LMB 50 mg vs LMB 100 mg) will be obtained. The null hypothesis of no treatment difference will be tested at the one-sided 0.05 significance level. Both untransformed and log-transformed ALT will be analyzed, with log-transformed baseline in lieu of untransformed baseline as a covariate when log-transformed ALT is analyzed. For log-transformed ALT analysis the ratio to baseline results obtained by back transformation will be reported.

Additionally a repeated measures ANCOVA treating all post dose adjustment measurements as missing will be performed as well if the number of patients with dose adjustment is not small (for example, >20%).

The cohort effect will be explored and a cohort-wise analysis may be performed as needed.

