11.4.2 Statistical model, hypothesis, and method of analysis

A Bayesian approach will be used to analyze the change from baseline to Week 12 in ALT, which is assumed to follow a normal distribution with a known variance for each treatment arm. An informative prior for the placebo treatment effect and a non-informative prior for the LMB763 treatment effect will be incorporated into the analysis. The variance and the informative prior will be based on historical control data from studies such as the FLINT trial ([Neuschwander-Tetri et al 2015](#)). Median estimates, credible intervals and posterior probabilities that the placebo-adjusted ALT reduction by an LMB763 dose is (a) greater than 0 and (b) greater than 19 U/L and/or another cutoff value will be provided within the Bayesian framework. As a sensitivity analysis, the posterior probabilities will be calculated for varying values of the effective sample size for the placebo prior. A further sensitivity analysis using different values of the common variance assumed in the likelihood function and the prior may be performed as needed. An analysis using SAS PROC MCMC without assuming the variance is known in the likelihood function may be performed as well.

Additionally a repeated measures analysis of covariance (ANCOVA) will be performed for change from baseline ALT without using historical placebo control data. The model will include effects for treatment, visit, treatment by visit interaction, stratification factor (BMI group), baseline, and baseline by visit interaction. An unstructured variance-covariance structure will be used to account for correlation among multiple measurements from the same patient and variance heterogeneity. Point estimates, the associated two-sided 90% confidence intervals as well as the p-values for treatment differences will be obtained. The null hypothesis of no treatment difference will be tested at the one-sided 0.05 significance level. Both untransformed and log-transformed ALT will be analyzed. For log-transformed ALT analysis the ratio to baseline results obtained by back transformation will be reported

The cohort effect will be explored and a cohort-wise analysis for both the Bayesian and ANCOVA approaches may be performed as needed.

If placebo data from in-house studies in a similar patient population become available they may be included in an ANCOVA on log-transformed data via informative priors.

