11.7 Sample size calculation

A mean decrease of 11 U/L from baseline to Week 12 in ALT was observed in the placebo group (N=142) of the FLINT trial. Historical placebo control data from trials such as the FLINT study will be used when analyzing ALT data from the current study by including prior information in a Bayesian approach.

Data from 54 patients in an LMB763 dosing arm and 54 placebo patients (placebo data from the current study supplemented by historical placebo control data), will provide approximately

76% power to detect a 19 U/L placebo-adjusted reduction from baseline ALT. The sample size calculation was done using a one-sided test at the 0.05 significance level, assuming a standard deviation of 41.16 U/L which was derived from the FLINT trial. A placebo-adjusted 19 U/L reduction in ALT corresponds to a 30 U/L decrease if the mean reduction induced by the placebo treatment is 11 U/L as reported in the FLINT study.

The corresponding power without using any historical placebo control data will be 61% if 54 patients in a LMB763 dosing arm and 27 patients in the placebo arm complete the study.

To make allowance for potential dropouts approximately 96 patients will be enrolled in the each dosing cohort. All patients who have been enrolled into the initial cohort will complete the protocol at that dose, however no further patients will be recruited into that cohort

Corporate Confidential Information

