6.1.5 Sensitivity analysis

As a sensitivity analysis the Bayesian analysis in [Section 6.1.3](#) will be repeated with varying values of the effective sample size for the placebo prior. A further sensitivity analysis using different values of the common variance assumed in the likelihood function and the prior may be performed as needed. A Bayesian analysis without assuming the variance is known in the likelihood function may be performed as well.

If more than 10% of the data for the Bayesian analysis on the change from baseline to Week 12 in ALT are missing then as a sensitivity analysis the Last Observation Carried Forward (LOCF) approach and/or another method may be used to impute missing data and the Bayesian analysis re-conducted.

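### The Bayesian analysis of Week 12 ALT fixes its variance from historical controls, so its interval width and posterior probabilities do not reflect this trial's own scatter; the Bayesian run that estimates the variance is only optional

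*SAP*

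**What the plan says.** The Bayesian part of SAP 6.1.3 models Week 12 change in ALT, "which is assumed to follow a normal distribution with a known variance for each treatment arm". On the source of that variance it says: "The variance and the informative prior will be based on historical control data from external and/or internal studies such as the FLINT trial". The placebo mean has an informative prior and the LMB763 mean a non-informative one. The outputs are medians, 90% credible intervals and the posterior probabilities of a placebo-adjusted reduction above 0 and above 19 U/L (or another cutoff). Protocol 11.4.2 describes the same model.

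The visible SAP text gives no number for the variance. Protocol 11.7 has one, for sample size only: "assuming a standard deviation of 41.16 U/L which was derived from the FLINT trial".

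SAP 6.1.5 makes one Bayesian sensitivity analysis firm, namely varying the effective sample size of the placebo prior. The runs that touch the variance are optional. One is a run "using different values of the common variance assumed in the likelihood function and the prior may be performed as needed". The other reads: "A Bayesian analysis without assuming the variance is known in the likelihood function may be performed as well". Protocol 11.4.2 names the software: "An analysis using SAS PROC MCMC without assuming the variance is known in the likelihood function may be performed as well".

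SAP 4 pools all placebo patients. SAP 6.1.3 also commits to a repeated-measures ANCOVA with an unstructured covariance and adjustment for "stratification factor (BMI group), baseline, and baseline by visit interaction".

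**The concern.** With a known variance, the posterior mean responds to the data but the posterior SD of a treatment difference does not. It depends only on the fixed SD, the numbers of patients and the prior. If patients here vary more than the historical controls did, the intervals are too narrow and the probabilities too extreme. If they vary less, the reverse holds.

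There are two reasons not to take the historical value for granted. It comes from control data but is also applied to the LMB763 arms. And the two cohorts enter at different ALT floors (60/40 IU/L for males/females in Cohort 1, 43/28 in Cohort 2; Protocol 4.1), so one historical SD need not suit both.

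This model is the only firm source of the two posterior probabilities. The one firm Bayesian sensitivity analysis varies the prior's weight, which leaves the likelihood variance untouched. The sponsor's team is unblinded throughout (Protocol 3.2 and 6.4), so a value and an option left open now could be settled after results are visible.

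**Working it through.** **Inputs.** From Protocol 11.7: SD 41.16 U/L, 54 LMB763 completers per dose, 27 concurrent placebo completers per cohort, target 19 U/L, one-sided 0.05, historical placebo group N = 142. From SAP 4: pooled placebo, so 2 × 27 = 54. Assumed: the fixed SD is 41.16; the prior is worth 27 patients (the number that brings 27 placebo patients to the planned 54); true SDs of 30, 41.16 and 50.

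**1. The plan's own power.** For 54 vs 54, SE = 41.16 × √(2/54) = 7.92 and 19/7.92 = 2.40, giving 77% (noncentral t). For 54 vs 27, SE = 41.16 × √(1/54 + 1/27) = 9.70 and 19/9.70 = 1.96, giving 62%. The stated figures are about 76% and 61%, so the inputs are read correctly.

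**2. Half-width with the SD fixed.** Half-width = 1.645 × 41.16 × √(1/54 + 1/(nC + 27)), where nC is the number of current placebo patients.
- Pooled placebo, nC = 54: 11.9 U/L.
- Protocol 11.7 planning case, nC = 27: 13.0 U/L.

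The observed SD does not appear in the formula.

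**3. Coverage of the nominal 90% interval.** Coverage = 2Φ(half-width/√V) − 1, with V = SD² × (1/54 + nC/(nC + 27)²) + (27/(nC + 27))² × pv. Here pv is the error variance of the prior mean: either 41.16²/27 = 62.7 (error matching the prior's stated weight) or 41.16²/142 = 11.9 (sampling error of the 142-patient group only).

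Example, pooled, SD 50, first pv: V = 2500 × 0.02675 + 62.7/9 = 66.9 + 7.0 = 73.8, √V = 8.59, 11.89/8.59 = 1.384, coverage 83.4%.

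| Case | pv | SD 30 | SD 41.16 | SD 50 |
|---|---|---|---|---|
| Pooled, 54 vs 54+27 | 41.16²/27 | 96.7% | 90.0% | 83.4% |
| Pooled, 54 vs 54+27 | 41.16²/142 | 98.2% | 91.8% | 85.0% |
| Planning, 54 vs 27+27 | 41.16²/27 | 95.9% | 90.0% | 84.2% |
| Planning, 54 vs 27+27 | 41.16²/142 | 98.6% | 93.5% | 87.4% |

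**4. Posterior probabilities.** Pooled case, taking the observed placebo mean equal to the prior mean. Under the plan the posterior SD is 7.23. If the trial's SD is used in the likelihood, the posterior variance is SD²/54 + 1/(54/SD² + 27/41.16²), so the posterior SD is 5.46 at SD 30 and 8.54 at SD 50.
- Posterior mean difference 12 U/L: P(>0) = Φ(12/7.23) = 0.951 at any spread, against Φ(12/5.46) = 0.986 and Φ(12/8.54) = 0.920.
- Posterior mean difference 25 U/L: P(>19) = Φ(6/7.23) = 0.797 at any spread, against Φ(6/5.46) = 0.864 and Φ(6/8.54) = 0.759.

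**5. What estimating the variance does.** Simulation of the planning case (20,000 trials per SD, prior variance 41.16²/27 on the placebo mean, flat prior on log SD, prior error as in the first pv) gives mean half-widths of 10.3, 13.1 and 15.1 U/L at SDs of 30, 41.16 and 50. Coverage is 90.2, 90.3 and 90.1%, with simulation error of about 0.2 points. The width now follows the scatter and coverage stays at its nominal level.

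**The case against.** The strongest reply is that a firm analysis already estimates the variance. The ANCOVA will be performed, is baseline-adjusted, and carries the only stated test; SAP 6.1.2 also tabulates observed SDs, so a poor assumed value would be noticed. The study is non-confirmatory and the visible text hangs no decision on the posterior probabilities. All of this stands and limits the weight of the point. It does not remove it, because the ANCOVA borrows no historical data and yields no posterior probabilities.

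The size is also assumed. The documents do not source true SDs of 30 or 50, and the intervals could turn out conservative. This stands too.

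A reader might infer more than the documents support:
- **That the missing covariates cause the problem.** They do not. Width ignores scatter because the variance is fixed. An unadjusted model also matches the unadjusted historical mean change of 11 U/L in Protocol 11.7.
- **That pooled placebo biases the dose contrasts of this model.** A simulation with no drug effect, assumed ALT mean 60 and SD 30, and the floor acting at screening gave a shift of 0.0–0.1 U/L for the unadjusted analysis. A shift of 0.7–1.0 U/L arose only after adding baseline adjustment with no cohort term.
- **That the SAP contradicts itself on the variance.** A single common value can be the known variance for each arm. The text needs clarifying, no more.
- **That no value was ever fixed.** SAP text between sections 2 and 4 is redacted, so the statement covers the visible text only.

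**Conclusion.** The point holds for the Bayesian analysis alone. Its intervals and probabilities are calibrated only if the historical SD happens to fit these patients, and the Bayesian run that would check this is not guaranteed. In the pooled analysis that SAP 4 describes, the half-width stays at 11.9 U/L. Coverage ranges from 96.7–98.2% at a true SD of 30 to 83.4–85.0% at 50, depending on the error in the prior mean. Probabilities move by a few hundredths (0.951 against 0.986 or 0.920 in the example). These figures rest on a fixed SD of 41.16, a prior worth 27 patients and the assumed true SDs; the direction of error is unknown.

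The impact is modest. It would go too far to say that the trial has no ALT result based on its own variance, since the ANCOVA provides one. The change is worth making because it costs little and uses a method that the protocol already names.

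**What to change.** In SAP 6.1.3, make the main Bayesian analysis the one that estimates the residual variance from the trial data, with PROC MCMC and the same placebo prior. State that prior as a mean and a variance. Keep the known-variance version as a sensitivity analysis in SAP 6.1.5, with its numeric value fixed in advance and a statement of whether it is common or arm-specific.

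Costs: SAP wording and slight extra programming. The estimated SD carries its own error, with 90% limits of about 0.92–1.10 times the estimate with 162 completers (chi-square, 159 df) and 0.89–1.15 with 81 (79 df). With the prior variance held at 41.16²/27, the prior's worth in current-trial patients becomes 27 × (SD/41.16)², about 14 at SD 30 and 40 at SD 50, so the effective-sample-size sensitivity analysis should be expressed through the prior variance.

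Baseline and BMI covariates, a cohort term and realignment of the prior are optional considerations and not part of this request. Baseline adjustment would need historical baseline ALT, which the documents do not give. A cohort term would widen the half-width from 11.9 to 13.0 U/L and lower power at 19 U/L from about 84% (54 vs 81) to 77% (54 vs 54), or to 62% (54 vs 27) for a cohort to which the prior is not applied.
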